5.5.1 Summary of Known Potential Risks with Study Medication

Vitamin E (study drug) is an essential nutrient found in highest quantities in sunflowers, almonds, hazelnuts, and peanuts. It is essential for the body's cells to function.

To our knowledge, there are two published studies with 800 IU/day of a-tocopherol, both in NAFLD and NASH (PIVENS and TONIC)

In the **PIVENS** trial, 84 adults with biopsy proven NASH were administered 800 IU/d of atocopherol for 96 weeks (Sanyal AJ, Chalasani N, Kowdley KV, et al. Pioglitazone, vitamin E, or placebo for nonalcoholic steatohepatitis. N Engl J Med 2010; 362:1675-1685

AEs by severity	Placebo	Attribution to Study	Vitamin E
	(N=83)	Drug Not Related	(N=84)
Mild	20	NOT NETALEU	24
Moderate	20	Not Related	19
Severe	10	Not Related	7
			Gastroenteritis 1;
			Hyperglycemia 1; Pain 3;
			Syncope 1; Urticaria 1
Life	0	Not Related	2
threatening			Cardiac ischemia/infarction
			1
			Liver dysfunction 1
Fatality	0	Not Related	1 (Cause of death:
			Pneumonia and liver failure
			secondary to sepsis from
			gram negative bacteremia.
			Deemed unrelated to the
			study drug).

In the TONIC trial (Lavine, 2011), 58 children with biopsy proven NAFLD received 800 IU/day of a-tocopherol for 96 weeks.

AEs by	Placebo	Attribution to Study	Vitamin E
severity	(N=58)	Drug	(N=58)
	(1, 20)	Not Related	
Mild	6		10
Moderate	12	Not Related	7
Severe	9	Not Related	3 (Bronchospasm 1, elevated blood glucose 1, hepatotoxicity 1); Note: No specific details of this Hepatotoxicity SAE are available from the publication. In this paper (supplemental table eTable2), it was reported that there was only one patient with ALT > 2 ULN in vitamin E group as opposed to 5 in placebo group (p=0.09). No cases of bilirubin > 3 mg/day in either group.

Vitamin E administered prophylactically or therapeutically within the range of the tolerable upper limit (i.e., ≤ 1000 mg) established for adults by the Institute of Medicine, has evidenced very low toxicity in humans. Summaries of the adverse events reported by double-blind randomized-controlled trials of vitamin E, including dl- α -tocopheryl acetate, are included in tables 5.5 and 5.6 of the dl- Alpha- Tocopherol Acetate Investigator's Brochure. Overall, oral

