10.3.2 Treatment and Holding/Stopping Rules for Drug Induced Liver Injury (DILI)

See the chart below for DILI monitoring and stopping guidelines:

Treatment Emergent ALT Elevation	Treatment Emergent Total	Liver Related	Management Recommendation
	Bilirubin	Symptoms	
Normal/near normal baseline: ALT ≥ 5 ×ULN Elevated baseline: ALT ≥3x baseline or ≥300 U/L whichever occurs first	Normal Patients with Gilbert's syndrome: No change in baseline total bilirubin	None	 Repeat ALT, AST, ALP, TBL, in 2-5 days. Follow-up for symptoms Initiate evaluation for other etiologies of abnormal liver tests
Normal/near normal	Normal	Severe	Repeat ALT, AST,
baseline: ALT ≥ 3 ×ULN Elevated baseline: ALT ≥2x baseline or ≥300 U/L whichever occurs first	Patients with Gilbert's syndrome: No change in baseline total bilirubin	fatigue, nausea, vomiting, right upper quadrant pain, tenderness, fever, rash, and/or eosinophilia (> 5%)	 ALP, TBL, in 2-5 days. Follow-up for symptoms Initiate evaluation for other etiologies of abnormal liver tests
Normal/near normal	Normal	None	Interrupt study drug
baseline: ALT ≥ ×8 ULN Elevated baseline: ALT ≥5x baseline or ≥500 U/L whichever occurs first	Patients with Gilbert's syndrome: No change in baseline total bilirubin		 Initiate close monitoring and workup for competing etiologies Study drug can be restarted only if another etiology is identified and liver enzymes return to baseline.
Normal/near normal baseline:	TBL > 2x ULN	Severe	Interrupt study drug
ALT ≥ ×3 ULN Elevated baseline: ALT ≥2x baseline or ≥300 U/L whichever occurs first	Patients with Gilberts syndrome: Doubling of direct bilirubin or increased INR to >1.5	fatigue, nausea, vomiting, right upper quadrant pain, tenderness, fever, rash, and/or eosinophilia (> 5%)	 Initiate close monitoring and workup for competing etiologies Study drug can be restarted only if another etiology is identified and abnormalities return to baseline.
Normal/near normal baseline:	Normal or Elevated	Severe	 Interrupt study drug Initiate close
ALT ≥ ×5 ULN		fatigue, nausea, vomiting,	 Initiate close monitoring and workup for
Elevated baseline: ALT > 3x baseline or > 300 U/L		right upper quadrant	competing etiologiesStudy drug can be restarted only
Drotocol no + 2017	Vorsion	Data	Dago 40 of 52

(whichever occurs first)	pain, tenderness, fever, rash, and/or eosinophilia (> 5%)	if another etiology is identified and abnormalities return to baseline.
-----------------------------	--	--

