10.3.3 Responsibilities

- The Principal Investigator (PI) ensures that SAE reporting procedures outlined in the study protocol are adhered to and that all required documentation is up-to-date and that regulatory and IRB/IEC SAE reporting procedures are followed.
- All study personnel at the study sites (Study Coordinator, Study Nurse, PI, or designee) who are in contact with clinical trial subjects are responsible for collecting AE information from the subject at each scheduled site visit or during telephone calls with the subject. Therefore, clinical research personnel or delegates (e.g. CRO) who initiate and monitor the study are responsible for explaining the procedures for reporting and evaluating AEs to the PI, and all study personnel who will be in contact with the subjects/patients.
- During the course of the study complete reports of all AEs should be entered in the subject's/patient's site source documents, and on the appropriate study case report forms (CRFs).
- A physician is responsible for: identifying and evaluating the severity (mild, moderate, or severe) and clinical importance of the AE, taking appropriate medical action(s), and for notifying a clinical research monitor, CRO and PV vendor immediately of an SAE, as specified in the protocol, and also for notifying the IRB/IEC. A copy of the source documents and related records should be supplied with the SAE report to the PV Vendor.
- Likewise, a physician indicates the causality (relationship) of the AE to the study product.
- For any laboratory abnormality, the PI will make a judgement as to its clinical significance. If the laboratory value is thought to be clinically significant, the IND Sponsor or medical monitor may be consulted, and an assessment will be made by the PI, as to its relationship to investigational product administration, and it will be documented on the AE page of the eCRF.

- The PI should comply with applicable regulatory requirement(s) related to the reporting of SAEs to the regulatory authority(ies) and the IRB /IEC.
- At completion of the study, the final lists of AEs and SAEs will be MedDRA coded by the CRO or PV vendor.

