# 3.3 Safety Objective(s)

To examine any treatment-emergent adverse event (TEAEs) and changes in clinical safety laboratory parameters. Safety will be assessed with vital signs, serum hematology and biochemistry, and AE/SAE reporting.

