#### 8.3 Secondary Endpoint Analyses

- The linear mixed model described in section 8.2 for the 6-month hepatic fact fraction [%] will also be used to estimate the difference between DHA EE and PBO, and vitamin E and PBO. The respective model derived pairwise comparisons will be estimated along with a 95% confidence interval. A Dunnett correction for multiple comparisons will be used.
- The between group differences in the anthropometric measures, liver enzymes, FIB-4 score, plasma Vitamin E (α-tocopherol), plasma DHA, and lipid panel will be estimated at 3 and 6 months with a linear mixed ANCOVA model. The respective follow-up measure, at each of 3 and 6 months, will be the response vector. Fixed effects will include the respective baseline anthropometric measure, intervention group, diabetes stratification, time point, and intervention group by time point interaction. Clinic site will be the random effect. Model derived pairwise comparisons of DHA EE + vitamin E vs. PBO, vitamin E vs. PBO, and DHA EE vs. PBO at 3 and 6 months will be estimated along with 95% confidence intervals. The Holm method will be used to adjust for the 6 planned comparisons (i.e. the LSMESTIMATE statement in SAS). Note, the purpose of the model is to estimate the effect at 3 and 6 months, adjusted for baseline, and not evaluate the trend which would require a joint test of intervention group and the intervention group by time interaction.
- At 6-month, the differences of each intervention group to PBO in insulin resistance measures, SF-36 domains, and inflammatory markers will be estimated with a linear mixed ANCOVA model. The respective baseline measure, intervention group, and baseline diabetes status will be included as fixed effects. Study site will be included as a random effect. Pairwise comparisons of DHA EE + vitamin E vs. PBO, vitamin E vs. PBO, and DHA EE vs. PBO will be estimated along with 95% confidence intervals. A Dunnett correction for multiple comparisons will be used.

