# 8.6 Safety Analysis

Adverse events (AEs) will be collected and classified according to the Common Terminology for Adverse Events (CTCAE) system. Note that each CTCAE v5.0 term is a MedDRA LLT (Lowest Level Term). All adverse events (AEs) will be summarized by intervention group according to the safety population. The number of subjects experiencing a given event will be summarized overall (i.e. any event of any grade) and by the maximum recorded grade. A separate listing will be provided of the subset of events that were indicated as serious adverse events (SAEs).

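### No planned output counts, by arm, the subjects who cross the liver-injury laboratory thresholds in Protocol 10.3.2

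*SAP*

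**What the plan says.** Protocol 10.3.2 opens its table with "See the chart below for DILI monitoring and stopping guidelines". Each of the five rows combines an ALT criterion, a bilirubin condition and a symptom condition. Two rows lead to repeat tests after a few days and three to interruption of study drug. For a subject with elevated baseline and no symptoms, the repeat-test criterion is "ALT ≥3x baseline or ≥300 U/L whichever occurs first" and the interruption criterion is "ALT ≥5x baseline or ≥500 U/L whichever occurs first".

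The analysis side reads as follows.

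- SAP 3.3 gives the safety objective: "To examine any treatment-emergent adverse event (TEAEs) and changes in clinical safety laboratory parameters".
- SAP 8.3 says that between-group differences in liver enzymes "will be estimated at 3 and 6 months with a linear mixed ANCOVA model". The response is the value at each of those two visits.
- Protocol 9.3.5 plans descriptive statistics for clinical chemistry by group and timepoint, plus least squares means with confidence intervals.
- SAP 8.6 deals with events only: "All adverse events (AEs) will be summarized by intervention group according to the safety population", overall and by maximum grade, with a listing of serious events.
- SAP 12.0 places the liver enzyme tables (7.1, 7.2) in the ITT and PP populations. For the safety population it lists only adverse events and serious adverse events (13.1, 13.2).
- The SAP 12.1 shells give median, quartiles, minimum and maximum by arm, for the value and for absolute and percentage change.
- Protocol 10.3.3 sets the route from laboratory value to adverse event: "For any laboratory abnormality, the PI will make a judgement as to its clinical significance". Protocol 7.1.3 adds that HH flags are used for ALT and AST.

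**The concern.** Drug-induced liver injury, if it occurs, affects a few subjects rather than shifting a whole arm. The useful safety questions are how many subjects per arm reached a threshold, whether ALT and bilirubin rose together in one person, and how often product was interrupted. The planned outputs answer none of these directly.

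The protocol uses this kind of statistic itself. In section 5.5.1 it puts the hepatotoxicity event in the earlier paediatric vitamin E trial into context with a by-arm count: "there was only one patient with ALT > 2 ULN in vitamin E group as opposed to 5 in placebo group". This trial's table list would not yield the equivalent figure.

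At stake is how well the laboratory half of the safety objective is answered. If counts are wanted after unblinding and none were pre-specified, the cut-offs would be chosen with the data in view. The same table would also serve a favourable result, because it could document that few or no subjects crossed.

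**Working it through.** **1. The plan's own figure.** Neither document states an expected number of liver-injury events. The nearest figure is the arm size (Protocol 9.3.7, SAP 7.0): difference 3.64, SD 7, two-sided alpha 0.05, power 80%. The normal approximation gives n = 2 x (1.960 + 0.842)^2 x 7^2 / 3.64^2 = 58.1, so 59 per arm. The t-test gives 59.03, so 60, with power 0.806 at n = 60. Then 180 / 0.90 = 200. The figures reproduce, and 60 is used below as the completing arm.

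**2. What each planned output can show.**

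| Output | Subjects crossing, by arm | ALT and bilirubin in the same subject | Unscheduled repeats |
|---|---|---|---|
| SAP 8.3 model | No, mean differences | No | No, 3 and 6 months only |
| SAP 12.1 shells | No, one extreme per visit | No | No |
| SAP 8.6 AE table | Only those recorded as AEs | No | Only if recorded as an AE |
| Table 1.1c | Discontinuations, not interruptions | No | No |

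**3. Can the mean fall while subjects cross?** Inputs:

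- Protocol 1.3.2 cites a fall of 7.42 U/L in ALT per 1 g/day of DHA. The dose is 1.89 g/day of DHA EE (Protocol 5.1.1). The high case is 7.42 x 1.89 = 14.0 U/L. The low case takes the effect of 1 g only, 7.4 U/L.
- Baseline ALT is at least 40 and below 250 U/L by the eligibility criteria, but no mean is given. I assume 60, 80 or 100 U/L.
- Thresholds are 3x baseline or 300 U/L, whichever is reached first (180, 240, 300), and 5x or 500 (300, 400, 500).

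With k subjects at the threshold and the other n - k falling, mean change = [k x (threshold - baseline) - (n - k) x fall] / n. This stays negative while k < n x fall / (threshold - baseline + fall). For n = 60, baseline 80, 3x threshold and fall 14.02: 60 x 14.02 / (160 + 14.02) = 4.8, so k can be at most 4.

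| Arm size, threshold | Fall 14.0: largest k at baseline 60 / 80 / 100 | Fall 7.4: largest k at baseline 60 / 80 / 100 |
|---|---|---|
| 60, 3x or 300 | 6 / 4 / 3 | 3 / 2 / 2 |
| 60, 5x or 500 | 3 / 2 / 2 | 1 / 1 / 1 |
| 30, 3x or 300 | 3 / 2 / 1 | 1 / 1 / 1 |

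**4. How such an arm would look in print.** Take n = 60, baseline 80, three subjects at 240 and 57 falling by 14.02. The mean change is (3 x 160 - 57 x 14.02) / 60 = -5.3 U/L. The largest percentage change would show as +200%. The SD from this two-point pattern alone is 174.02 x sqrt(3 x 57 / (60 x 59)) = 38.2. The 95% half-width is then 1.96 x 38.2 / sqrt(60) = 9.7, and the interval is about -15.0 to +4.4 U/L before any other variation. With a fall of 7.42 the same three subjects give a mean of +0.95 U/L.

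**5. What a count would show.** Three of 65 randomised subjects is 4.6%, exact 95% interval 1.0% to 12.9%. That is imprecise, but it is on the scale of the question.

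**The case against.** A reader might infer that liver laboratory values are analysed only as arm means, and that the trial could announce a liver-enzyme benefit in an arm containing several cases of liver injury. The documents do not support that.

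- Range, quartiles, and the extremes of absolute and percentage change are planned by arm, so a single very high value would be visible.
- The masking is fragile. With 65 subjects, three rising by 240 U/L and 62 falling by 14.02, the mean change is -2.3 U/L, with SD 53.7 and a half-width of about 13. With a fall of 7.42 the mean becomes +4.0. Neither would be reported as a benefit on the untransformed scale. The planned estimate is also a difference from placebo, which a one-arm calculation does not reproduce.
- Adverse events include abnormal laboratory findings and are counted by arm and maximum grade. Three of the five rows in Protocol 10.3.2 require severe symptoms, which are events in their own right. A DSMB also reviews safety data.
- Section 5.5.1 attributes the earlier events as unrelated to study drug, and its ALT count favours vitamin E. There is no ground there for expecting harm.

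All of this stands, and it limits the size of the point. It does not supply the count. The extremes show one subject per visit. The two asymptomatic rows depend on the investigator's judgement of the laboratory value. CTCAE grades are not mapped to the table's criteria, some of which are relative to baseline.

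A practical objection also stands in part. Section 10.3.2 does not define where a near-normal baseline ends and an elevated one begins. A laboratory-only count cannot reproduce rows that need symptoms. The documents do not confirm an eCRF field for interruption under this table.

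**Conclusion.** The gap is confirmed and modest. Nothing in SAP 8.6, SAP 12.0 or Protocol 9.3.5 counts subjects per arm against the laboratory criteria of Protocol 10.3.2, joint ALT and bilirubin rises, or product interruptions. The gap lies in the safety section and the table list. The SAP 8.3 model is a legitimate efficacy analysis and contains no error.

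The masking figures (up to 6 / 4 / 3 subjects, or 3 / 2 / 2 with the smaller fall) show that a falling mean is no assurance. They do not show that injury would be hidden or that any is expected. They rest on an assumed baseline ALT, linear scaling of the cited per-gram effect, 1.89 g of DHA EE counted as 1.89 g of DHA in the high case, and no added vitamin E effect, because the documents give its direction but no size.

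**What to change.** Add to SAP 8.6 and SAP 12.0 one descriptive table by arm in the safety population, using scheduled and unscheduled post-baseline values.

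- Give the number and percentage of subjects, with exact 95% intervals, whose worst value met each ALT and bilirubin laboratory criterion already in Protocol 10.3.2, alone and jointly. Show how many subjects had no post-baseline sample.
- State in the table that it covers the laboratory component only, and which classification of baseline ALT is applied.
- Add the number with product interrupted under that section, where recorded.
- Add a plot of each subject's peak ALT (multiple of baseline) against peak total bilirubin (multiple of ULN).

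Keep the ANCOVA. No threshold, management rule, sample size or alpha changes. The cost is SAP wording, one table and one figure, mostly from data already collected. Before finalising, check that repeat tests done at local laboratories and product interruptions are captured in the database. Counts will be small and should be read descriptively.

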9.3.3 Secondary endpoint variable(s) and analyses

- Differences in hepatic fat fraction [%], measured by MRI-PDFF after 6 months of intervention, between DHA and placebo will be estimated with the same model as the primary endpoint. The estimated difference will be displayed with its 95% confidence interval.
- Differences in hepatic fat fraction [%], measured by MRI-PDFF after 6 months of intervention, between Vitamin E and placebo will be estimated with the same model as the primary endpoint. The estimated difference will be displayed with its 95% confidence interval.
- Between group differences in anthropometric measures, after 3 and 6 months of DHA EE and/or Vitamin E intervention will be analysed with the same approach as the primary endpoint, using the relevant anthropometric measure at baseline as the respective baseline covariate and gender as a categorical covariate.
- Between group differences in inflammatory markers after 6 months of intervention and liver enzymes after 3 and 6 months of DHA EE and/or Vitamin E intervention will be analysed with the same approach as above and diabetes status as a categorical covariate included in the model.
- Between group differences in the FIB-4 score after 6 months of DHA EE and/or Vitamin E intervention will be analysed with the same approach as above.
- \circ Between group differences in plasma DHA and plasma α -tocopheryl after 3 and 6 months of intervention will be analysed with the same approach as above.
- Between group differences in SF-36 quality of life score after 6 months of DHA EE and/or Vitamin E intervention will be analyzed by ANCOVA with baseline score included in the model.
- Between group differences in dietary intake of LC-PUFA (i.e. DHA and EPA) will be assessed by the FFQ and analysed over time by repeated measures ANOVA with baseline level and site included in the model.

With blinded data, the residuals of the models will be analysed visually (QQ-plots, residual plots) to determine if the model assumptions (normality, variance homogeneity) are met. If necessary, variance-stabilizing transformations or non-parametric methods will be considered.

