# 8.1 Demographic and Baseline Variables

Subject demographics of randomized subjects will include age, sex, diabetes strata, ethnicity, and race collected at the first screening visit overall and by treatment assignment. Summary demographics will be provided by treatment group for the study populations defined in section 6.0.

The following describes the time point used as the baseline measures for the outcome variables:

- Baseline hepatic fat fraction[%] as measured by MRI-PDFF is collected at the second screening visit (Visit 1)
- Baseline anthropometric measures are collected at the first screening visit (Visit 0)
- Baseline HbA1c, fasted insulin and fasting glucose are collected at the first screening visit (Visit 0)
- Baseline liver enzymes (AST, ALT, ALK-P) and bilirubin are collected at the first and second screening visits with the allowance for a 3rd unscheduled pre-treatment visit. The measurement closest to the date of randomization will serve as the baseline measure.
- Baseline Fibrosis-4 score is collected at the first screening visit (Visit 0)
- Baseline plasma vitamin E and DHA concentrations are collected at the second screening visit (Visit 1)
- The baseline lipid panel profile is collected at the second screening visit (Visit 1)
- The baseline responses to the short-form health survey (SF-36) is collected at the randomization visit (Visit 2)
- The baseline food frequency questionnaire (FFQ) for the LC-PUFA is collected at the randomization visit (Visit 2)
- Baseline inflammatory markers are collected at the second screening visit (Visit 1)
- Baseline AUDIT questionnaire total score collected at the first screening visit (Visit 0)

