|           | 6-month estimate
(95 % Cl)    |     |                       |        |           |
|           | 6-month difference ++ |     |                       |        |           |
|           | 95% CI                           |     |                       |        |           |
|           | p-value*                         |     |                       |        |           |
|           | adjusted p-value**               |     |                       |        |           |

+ Mixed model for repeated measures ANCOVA

++ Model derived estimated difference from the PBO; computationally equivalent to the estimated

difference from placebo in the change from baseline

\* p-value for the pairwise comparisons to the PBO

\*\* Holm correction for multiple comparisons between arms at multiple time points

|         |             |                   | РВО | DHA EE +
vitamin E | DHA EE | vitamin E |
|---------|-------------|-------------------|-----|-----------------------|--------|-----------|
| 3-Month | Absolute    | N                 |     |                       |        |           |
|         | change from | mean (sd)         |     |                       |        |           |
|         | Baseline    | median (min, max) |     |                       |        |           |
|         |             | Q1, Q3            |     |                       |        |           |
|         | Percentage  | N                 |     |                       |        |           |
|         | change from | mean (sd)         |     |                       |        |           |
|         | Baseline    | median (min, max) |     |                       |        |           |
|         |             | Q1, Q3            |     |                       |        |           |
| 6-Month | Absolute    | N                 |     |                       |        |           |
|         | change from | mean (sd)         |     |                       |        |           |
|         | Baseline    | median (min, max) |     |                       |        |           |
|         |             | Q1, Q3            |     |                       |        |           |
|         | Percentage  | N                 |     |                       |        |           |
|         | change from | mean (sd)         |     |                       |        |           |
|         | Baseline    | median (min, max) |     |                       |        |           |

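### SAP 8.3 names a baseline anthropometric measure as the covariate for liver enzymes, FIB-4, plasma vitamin E, plasma DHA and lipids; it should name each outcome's own baseline

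*SAP*

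**What the plan says.** SAP 8.3, second bullet, opens with the outcomes it covers: "The between group differences in the anthropometric measures, liver enzymes, FIB-4 score, plasma Vitamin E (α-tocopherol), plasma DHA, and lipid panel will be estimated". The time points are months 3 and 6. One sentence then fixes the model for all of them: "Fixed effects will include the respective baseline anthropometric measure, intervention group, diabetes stratification, time point, and intervention group by time point interaction". Site is the random effect. No other baseline covariate is named.

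Other parts of the SAP bear on the same model:

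- Later in the bullet: "the purpose of the model is to estimate the effect at 3 and 6 months, adjusted for baseline".
- The third bullet, on insulin resistance, SF-36 and inflammatory markers: "The respective baseline measure, intervention group, and baseline diabetes status will be included as fixed effects".
- SAP 8.1 defines a baseline for each of the five non-anthropometric families. For liver enzymes and bilirubin, "The measurement closest to the date of randomization will serve as the baseline measure". For FIB-4 it is the Visit 0 value. For plasma vitamin E, plasma DHA and lipids it is the Visit 1 value.
- The footnote to the repeated-measures shell in SAP 12.1 begins "Model derived estimated difference from the PBO; computationally equivalent to the estimated" and goes on to name the placebo difference in change from baseline. The shell for 6-month outcomes has a similar footnote.

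Protocol 9.3.3 analyses the anthropometric outcomes by the primary approach, "using the relevant anthropometric measure at baseline as the respective baseline covariate", with gender added. It then refers back to that approach for liver enzymes, inflammatory markers, FIB-4 and plasma levels.

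**The concern.** For weight, waist circumference, waist-to-hip ratio and BMI, the named covariate is the outcome's own baseline. For ALT, FIB-4, plasma DHA or LDL it is a different variable. It is also not a defined one: SAP 4.2 lists four anthropometric measures, and none of them corresponds to ALT or LDL.

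An analyst must therefore choose. Using own baseline departs from the written text for five secondary families, and SAP 9.0 requires deviations to be described and justified. Choosing an anthropometric covariate follows the text, but it gives up the precision that baseline adjustment is meant to bring and leaves chance baseline differences in the outcome inside the contrast. It also makes the change-from-baseline footnote untrue wherever it applies.

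**Working it through.** **Plan's own figure.** The documents give no precision or power figure for these secondary models. The only sample-size figure, 60 per main arm (SAP 7.0: difference 3.64, SD 7, two-sided 0.05), is for the primary endpoint. It reproduces: exact t-test power is 0.7998 at 59 per arm and 0.806 at 60. This point does not touch it.

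**Step 1: the equivalence footnote.** Let Y be follow-up, B its own baseline and G the treatment group.

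- With own baseline: Y = a + bG + cB + e. Subtracting B from both sides gives Y − B = a + bG + (c − 1)B + e. The treatment coefficient b is the same, so the footnote is true.
- With an anthropometric covariate A instead of B, this step is not available. The follow-up and change-score estimates differ by the chance imbalance in B between arms, adjusted for A.

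In one simulated data set (60 vs 60), own baseline gave 0.0098 for both estimates. The anthropometric covariate gave 0.0834 for follow-up and −0.0275 for change, a gap of 0.0834 + 0.0275 = 0.1109 that is pure baseline imbalance.

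**Step 2: precision.** Let ρ be the correlation of follow-up with its own baseline, and r its correlation with the anthropometric baseline. Neither is in the documents, so both are assumed. At one time point, ignoring site and diabetes, the ANCOVA residual variance is proportional to 1 minus the squared correlation. Hence:

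variance ratio (as written / own baseline) = (1 − r²)/(1 − ρ²), and the SE factor is its square root.

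Example with ρ = 0.5 and r = 0.2: (1 − 0.04)/(1 − 0.25) = 0.96/0.75 = 1.28, and √1.28 = 1.13.

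| SE factor | ρ = 0.3 | 0.5 | 0.6 | 0.7 | 0.8 |
|---|---|---|---|---|---|
| r = 0 | 1.05 | 1.15 | 1.25 | 1.40 | 1.67 |
| r = 0.2 | 1.03 | 1.13 | 1.22 | 1.37 | 1.63 |
| r = 0.3 | 1.00 | 1.10 | 1.19 | 1.34 | 1.59 |

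Confidence intervals widen by about the same factor.

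**Step 3: bias and chance imbalance.** This was checked with 4,000 simulated trials (60 vs 60, no treatment effect, correlation 0.2 between the anthropometric measure and the outcome's own baseline).

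- The mean estimate was about 0 under both models, so neither is biased.
- At ρ = 0.5 the SE rose from 0.1581 to 0.1818 SD, a factor of 1.15. At ρ = 0.7 it rose from 0.1307 to 0.1811, a factor of 1.39. Here r with follow-up is 0.2ρ, that is 0.10 and 0.14, and the formula gives the same factors.
- Under the written model, the estimate correlated 0.48 (ρ = 0.5) and 0.66 (ρ = 0.7) with the chance baseline difference in the outcome. With own baseline the correlation was about 0.

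**The case against.** The strongest reply is that this is one stray word and not an analysis choice. The same bullet promises baseline adjustment, SAP 8.1 defines an own baseline for every family, the next bullet has the right wording, and the footnotes presuppose it. The literal model cannot even be run without a further choice. As an account of intent this stands. It does not remove the point, because the sentence is the stated model rule and nothing expressly overrides it.

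Four stronger readings are tempting, and the documents do not support them:

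- **That the secondary contrasts would be biased.** They would not. Randomization protects them, and only precision and control of chance imbalance suffer.
- **That these outcomes lose a definite amount of power.** The documents state no power for them and no correlations. Power computed at an unadjusted 0.05 would also ignore the Holm adjustment over six comparisons that this bullet specifies. If the anthropometric measure predicts follow-up as well as own baseline does (both 0.3), nothing is lost.
- **That protocol 9.3.3 makes the same error.** This is doubtful. Its wording can be read as the primary approach with each outcome's own baseline put in. The protocol bullet that refers back for liver enzymes also covers inflammatory markers, and the SAP analyses those with their own baseline. Lipids have no bullet in 9.3.3 at all; they appear in 9.3.5.
- **That the repeated-measures footnote would be false for all five families.** That shell is for outcomes collected at baseline, 3 and 6 months. Lipids and FIB-4 are scheduled only at baseline and 6 months, so it does not clearly govern them. The 6-month shell carries a similar footnote, but it is not explicitly tied to them.

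**Conclusion.** The covariate named in SAP 8.3, second bullet, is wrong for liver enzymes, FIB-4, plasma vitamin E, plasma DHA and lipids. Own baseline was evidently intended, and the likely cause is wording carried over from the anthropometric outcomes. Followed literally, the model would give unbiased but less precise contrasts that retain chance baseline imbalance and do not equal the difference in change from baseline.

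The size cannot be fixed from the documents. Over assumed correlations of 0.3 to 0.8 with own baseline and 0 to 0.3 with the anthropometric measure, the standard error is larger by a factor of 1.0 (no loss) to about 1.67. The calculation treats one time point at a time and leaves out site and diabetes.

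The anthropometric outcomes are correctly specified. The primary endpoint, the hepatic-fat secondary contrasts and the third-bullet outcomes are not affected.

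**What to change.** In SAP 8.3, second bullet, replace the reference to a baseline anthropometric measure with: *the baseline value of the outcome being analysed (as defined in 8.1)*. The bullet then agrees with its own stated purpose, with the third bullet and with the SAP 12.1 footnotes, and the intended analysis need not be reported as a deviation under SAP 9.0.

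The cost is one phrase. The baselines are already collected and defined, no procedure changes, and no protocol amendment is needed for this point.
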